APPENDIX 2. PARTIAL DATE CONVENTIONS

ALGORITHM FOR TREATMENT EMERGENCE OF ADVERSE EVENTS

Imputed dates will not be presented in the listings.

Start Date	Stop Date	Action
Known	Known	
If start date < study med start date, then not TEAE
 
If study med start date ≤ AE start date ≤ the later of (study med stop +28 days or the safety follow-up visit), then TEAE
 
If the later of (study med stop +28 days or the safety follow-up visit) < AE start date, then not TEAE

	Partial	
If start date < study med start date, then not TEAE
 
If study med start date ≤ AE start date ≤ the later of (study med stop +28 days or the safety follow-up visit), then TEAE
 
If the later of (study med stop +28 days or the safety follow-up visit) < AE start date, then not TEAE

	Missing	
If start date < study med start date, then not TEAE
 
If study med start date ≤ AE start date ≤ the later of (study med stop +28 days or the safety follow-up visit), then TEAE
 
If the later of (study med stop +28 days or the safety follow-up visit) < AE start date, then not TEAE

Partial, but known components show that it cannot be on or after study med start date	Known	Not TEAE
	Partial	Not TEAE
	Missing	Not TEAE
Partial, could be on or after study med start date	Known	
If stop date < study med start date, then not TEAE
 
If study med start ≤ AE stop date ≤ the later of (study med stop +28 days or safety follow-up visit), then TEAE
 
If the later of (study med stop +28 days or safety follow-up visit) < AE stop date, then TEAE

Start Date	Stop Date	Action
	Partial	
Impute stop date as latest possible date (i.e. last day of month if day unknown or 31st December if day and month are unknown), then:
 
If stop date < study med start date, then not TEAE
 
If study med start ≤ AE stop date ≤ the later of (study med stop +28 days or the safety follow-up visit), then TEAE
 
If the later of (study med stop +28 days or the safety follow-up visit) < AE stop date, then TEAE

	Missing	Assumed TEAE
Missing	Known	
If stop date < study med start date, then not TEAE
 
If study med start ≤ AE stop date ≤ later of (study med stop +28 days or the safety follow-up visit date), then TEAE
 
If the later of (study med stop +28 days or safety follow-up visit date) < AE stop date, then TEAE

	Partial	
Impute stop date as latest possible date (i.e. last day of month if day unknown or 31st December if day and month are unknown), then:
 
If stop date < study med start date, then not TEAE
 
If study med start ≤ AE stop date ≤ the later of (study med stop +28 days or safety follow-up visit date), then TEAE
 
If the later of (study med stop +28 days or safety follow-up visit date) < AE stop date, then TEAE

	Missing	Assumed TEAE

ALGORITHM FOR PRIOR/CONCOMITANT/POST MEDICATIONS

Note: Separate flags will be assigned for prior, concomitant, and “post” medications. It is possible for a medication to be considered a prior medication, a concomitant medication, or both, depending on when the medication was used. However, only medications that began post-treatment will be flagged as “post”.

Note: Although a prior medication flag is defined here, prior medications will not be summarized in tables.

Rule	Rule Type	Start Date	Stop Date	Action
1	GENERAL	N/A	N/A	Apply all general imputation rules to start and stop dates as indicated. Use the known actual dates and the imputed dates to derive each medication flag as described in the remaining specifications.
2	GENERAL	All cases	Missing	If the stop date is missing, assume the medication is ONGOING unless otherwise directed by the Medical Monitor for a particular medication. (For example, a medication which is used only during surgery and which has a missing stop date might be treated as started and stopped on the same day. The instruction would be applied to all instances in which this occurred, not just an individual case.)
3	GENERAL	All cases	Partial	Impute a partial stop date as latest possible date (i.e. last day of month if day unknown or 31 st December if day and month are unknown)
4	GENERAL	Missing	All cases	If the start date is missing, assume the medication was ongoing prior to first dose.
5	GENERAL	Partial	All cases	Impute a partial start date as earliest possible date (i.e. first day of month if day unknown or 1 st January if day and month are unknown).
Prior medications are medications that were used before the first dose of study drug was administered.				
6	PRIOR	Known (Actual) or Partial (Imputed)	Known (Actual) or Partial (Imputed)	If (medication start date < date of first dose) then assign as prior='Yes'. If (medication start date = date of first dose and medication stop date = date of first dose) then assign as prior='No'. If (medication start date ≥ date of first dose) and (medication stop date is > date of first dose) then assign as prior='No'.

Rule	Rule Type	Start Date	Stop Date	Action
7	PRIOR	Known (Actual) or Partial (Imputed)	Missing	If (medication start date < date of first dose) then assign as prior='Yes'; If (medication start date ≥ date of first dose) then assign as prior='No'.
8	PRIOR	Missing	Known (Actual) or Partial (Imputed)	If missing (medication start date) then assign as prior='Yes'.
9	PRIOR:	Missing	Missing	If missing (medication start date) then assign as prior='Yes',

Concomitant medications are medications which were used during the period of treatment with study drug, including:
 
 • Medications that started prior to C1D1 and ended (or were ongoing) on or after C1D1 • Medications that started and ended on C1D1 • Medications that started on or after C1D1 and before a decision to discontinue treatment for AGS-16C3F subjects or before the last dose of study medication for axitinib subjects. 				
10	CONCOMITANT	Known (Actual) or Partial (Imputed)	Known (Actual) or Partial (Imputed)	
If (medication stop date < date of first dose) then assign as concomitant = 'No'.
 
If (medication start date = date of first dose) and (medication stop date = date of first dose) then assign as concomitant = 'Yes'.
 
AGS: If (medication start date < date of decision to end treatment) then assign as concomitant = 'Yes'.
 
AGS: If (medication start date = date of decision to end treatment) and (medication stop date = date of decision to end treatment) then assign as concomitant = 'Yes'.
 
AGS: If (medication start date > date of decision to end treatment) then assign as concomitant = 'No'.
 
AXI: If (medication start date < date of last dose) then assign as concomitant = 'Yes'.
 
AXI: If (medication start date = date of last dose) and (medication stop date = date of last dose) then assign as concomitant = 'Yes'.
 
AXI: If (medication start date > date of last dose) then assign as concomitant = 'No'.

Rule	Rule Type	Start Date	Stop Date	Action
11	CONCOMITANT	Known (Actual) or Partial (Imputed)	Missing	AGS: If medication start date < date of decision to end treatment then assign as concomitant = 'Yes'. AXI: If medication start date < date of last dose then assign as concomitant = 'Yes'.
12	CONCOMITANT	Missing	Known (Actual) or Partial (Imputed)	If (medication stop date < date of first dose), assign as concomitant='No'. If (medication stop date ≥ date of first dose), assign as concomitant='Yes'.
13	CONCOMITANT	Missing	Missing	Assign as concomitant='Yes',
Post-treatment (or "post") medications are medications that began on or after the date of a decision to discontinue study drug for AGS-16C3F subjects or after the last dose of study drug for axitinib subjects.				
13	POST	Known (Actual) or Partial (Imputed)	Known (Actual) or Partial (Imputed)	AGS: If (medication start date ≤ date of decision to end treatment) then post='No'. AGS: If (medication start date ≥ date of decision to end treatment) and (medication stop date > date of decision to end treatment) then post='Yes.' AXI: If (medication start date ≤ date of last dose) then post='No'. AXI: If (medication start date ≥ date of last dose) and (medication stop date > date of last dose) then post='Yes.'
14	POST	Known (Actual) or Partial (Imputed)	Missing	AGS: If (medication start date ≥ date of decision to stop treatment) then assign as post="Yes". AGS: If (medication start date < date of decision to stop treatment) then assign as post="No". AXI: If (medication start date ≥ date of last dose) then assign as post="Yes". AXI: If (medication start date < date of last dose) then assign as post="No".
15	POST	Missing	Known (Actual) or Partial (Imputed)	If the medication start date is missing, assign as post='No'.

Rule	Rule Type	Start Date	Stop Date	Action
16	POST	Missing	Missing	If the medication start date is missing, assign as post='No'.

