## **5.7 Adverse Events and Other Safety Aspects**

### **5.7.1 Definition of Adverse Events (AEs)**

An AE is defined as any untoward medical occurrence in a subject administered a study drug or has undergone study procedures and which does not necessarily have a causal relationship with this treatment. An AE can therefore be any unintended sign (including an abnormal laboratory finding), symptom, or disease temporally associated with the use of a medicinal (investigational) product, whether or not related to the medicinal (investigational) product.

This definition is broadened in this study to include any such occurrence (e.g., sign, symptom, or diagnosis) or worsening of pre-existing medical condition. Worsening indicates that the pre-existing medical condition has increased in severity, frequency, or duration of the condition or an association with significantly worse outcomes.

Interventions for pretreatment conditions (e.g., elective cosmetic surgery) or medical procedures that were planned before study enrollment are not considered AEs.

Some countries may have additional local requirements for events that are required to be reported as AEs or in an expedited manner similar to an SAE. In these cases, it is the investigator's responsibility to ensure these AEs or other reporting requirements are followed and the information is appropriately recorded in the eCRF accordingly.

An abnormality identified during a medical test (e.g., laboratory parameter, vital sign, ECG data, physical exam) should be defined as an AE only if the abnormality meets one of the following criteria:

- Induces clinical signs or symptoms
- Requires active intervention
- Requires interruption or discontinuation of study medication
- The abnormality or investigational value is clinically significant in the opinion of the investigator.

Disease progression should not be reported as an AE. Rather signs and symptoms associated with disease progression should be reported.

All AEs occurring after the first dose of investigational product observed by the investigator or reported by the subject (whether or not attributed to investigational product), will be reported in the eCRF. AEs will continue to be reported in the eCRF until 28 days post last dose, or at the subject's Safety Follow-Up visit, whichever occurs later. SAEs and medically significant AEs considered related to the investigational product by the investigator or the

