19.1. ADVERSE EVENTS

Treatment emergent adverse events (TEAEs) are defined as AEs that started or worsened in severity after the first dose of study drug and until 28 days post the last administration of the study drug or the subject's Safety Follow-Up visit, whichever occurred later. Events that begin on Day 1 will be counted as treatment-emergent.

AEs will be coded to system organ class (SOC) and preferred term (PT) using the Medical Dictionary for Regulatory Activities (MedDRA) Version 18.1 central coding dictionary and will be graded according to the National Cancer Institute (NCI) Common Toxicity Criteria for Adverse Events (CTCAE), version 4.03.

All summaries of AEs will include only treatment-emergent events unless otherwise stated.

Safety will be evaluated based on the incidence of AEs (including Grade 3 and Grade 4 AEs, treatment-related adverse events, serious adverse events, and AEs requiring discontinuation of study treatment). The number and percentage of AEs, SAEs, AEs leading to discontinuation of study treatment, and AEs related to study drug will be summarized by SOC, PT and treatment group. The number and percentage of AEs by severity will also be summarized. Listings of AEs, SAEs, deaths, and events leading to discontinuation of study treatment will be presented.

See Appendix 2 for handling of partial dates for AEs. In the case where it is not possible to define an AE as treatment emergent or not, the AE will be classified by the worst case; i.e. treatment emergent.

An overall summary of the number and percentage of subjects who had events in each of the categories described below will be produced by treatment group and for combined treatment groups.

- Subjects with at least one AE
- Subjects with at least one possibly drug-related AE
- Subjects with at least one AE of CTCAE Grade 3 or Grade 4
- Subjects with at least one possibly drug-related AE of CTCAE Grade 3 or Grade 4
- Subjects with at least one serious AE
- Subjects with at least one possibly drug-related serious AE
- Subjects whose treatment had to be modified due to an AE
- Subjects whose treatment had to be modified due to a possibly drug-related AE
- Subjects who discontinued treatment with study drug because of an AE
- Subjects who discontinued treatment with study drug because of a possibly drug-related AE
- Subjects with at least one AE resulting in death

- Subjects with at least one possibly drug-related AE resulting in death

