Listings will include TEAEs and Non-TEAEs. Any AE that was reported with a start date on or after the initiation of non-protocol anticancer treatment will be flagged in the listings.

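### SAP Appendix 2 has no worsening branch, so a pre-existing condition that worsens on treatment but keeps its pre-dose onset date is left out of the TEAE tables that SAP 19.1 says should count it

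*SAP*

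**What the plan says.** SAP 19.1 gives the definition: "Treatment emergent adverse events (TEAEs) are defined as AEs that started or worsened in severity after the first dose of study drug". The window closes at the later of 28 days after the last administration and the Safety Follow-Up visit. The same section restricts the tables: "All summaries of AEs will include only treatment-emergent events unless otherwise stated". It also says "Listings will include TEAEs and Non-TEAEs".

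SAP Appendix 2 turns the definition into an algorithm. Its rows are indexed by the state of the start date and of the stop date:

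- Known start, with the stop date known, partial or missing (three rows): "If start date < study med start date, then not TEAE".
- "Partial, but known components show that it cannot be on or after study med start date" (three rows): not TEAE for each type of stop date.
- "Partial, could be on or after study med start date", or start date missing: TEAE, unless the stop date falls before first dose.

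Protocol 5.7.1 extends the meaning of an adverse event: "This definition is broadened in this study to include any such occurrence (e.g., sign, symptom, or diagnosis) or worsening of pre-existing medical condition". It collects events occurring after first dose and lists the attributes that the investigator assigns. The only dates among these are onset and resolution. It does not say whether the onset of a worsened condition is the original date or the date of worsening.

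**The concern.** The definition has two routes to TEAE status: a new start, or a worsening. The algorithm implements only the first. One flag then governs the overall incidence tables and the summaries of serious events (SAP 19.1.3), Grade 3 and 4 events (19.1.4) and events leading to discontinuation (19.1.2), so an error in the flag carries into all of them.

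The population makes worsening plausible. Eligibility (Protocol 3.2 and 3.3) admits a uPCR below 2.0, excludes hypertension only when it is uncontrolled, and rules out hypothyroidism only when there are clinical symptoms. Toxicities from earlier approved drugs need only have stabilized. The drugs' known effects overlap with these conditions. Fatigue was reported in 71% of Phase 1 subjects on AGS-16C3F (Protocol 1.3.1.2). In the pooled axitinib data, hypertension was reported in 51%, fatigue in 45%, hypothyroidism in 25% and proteinuria in 21% (Protocol 1.3.2). These are on-treatment frequencies, not baseline prevalences, so they show where the problem could arise, not how often. Either arm could lose events, and not necessarily equally.

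**Working it through.** The plan states no figure on this point, so there is nothing to reproduce. The check applies the two rules to the same records. First dose is Day 1. For illustration, worsening occurs on Day 30 and the TEAE window ends on Day 120.

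| Record | SAP 19.1 | Appendix 2 |
|---|---|---|
| 1. Known start Day −20, stop known, worsens Day 30 | TEAE | not TEAE |
| 2. Known start Day −20, stop missing, worsens Day 30 | TEAE | not TEAE |
| 3. Partial start, certainly pre-dose, worsens Day 30 | TEAE | not TEAE |
| 4. Partial start, possibly on or after first dose, stop Day 60, worsens Day 30 | TEAE | TEAE |
| 5. Start missing, stop Day 60, worsens Day 30 | TEAE | TEAE |
| 6. New record opened at the worsening, start Day 30 | TEAE | TEAE |
| 7. Known start Day −20, no worsening | not TEAE | not TEAE |

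The rules conflict in cases 1 to 3 and agree in the rest. The conflict needs both a start that is certainly pre-dose and a later worsening held on that same record.

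The worst-case fallback in SAP 19.1 does not help. It applies only when treatment emergence cannot be determined, and a certain pre-dose start is determined.

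What remains visible outside the AE tables:

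- Laboratory: SAP 19.3.5 gives CTCAE shift tables from baseline to worst grade for the analytes in Table J, which include hemoglobin. Table J includes neither uPCR nor the thyroid tests.
- Eye: SAP 19.1.6 and 19.7.1 tabulate examination findings and visual acuity change separately. SAP 19.7.2 tabulates questionnaire symptoms, including dry eye, by worst post-baseline severity.
- Vital signs: SAP 19.5.3 summarizes weight change only; blood pressure is listed.
- Fatigue has no table outside the AE summaries.

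Size: for a given AE term, the share of subjects lost is p × w × r, where p is the share with the condition at baseline, w the share of those who worsen, and r the share of worsenings kept under the original onset date. The documents give none of the three. With p = 0.20 and w = 0.5, both assumed, the loss is 0.20 × 0.5 × r. That is 0% at r = 0, 2.5% at r = 0.25 and 10% at r = 1. This shows how the result depends on r; it is not an estimate.

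**The case against.** The strongest reply is that Protocol 5.7.1 makes the worsening itself the adverse event. Its natural onset is then the date of worsening, and the underlying condition belongs in medical or ocular history. Recorded that way it is case 6, and nothing is lost. The SAP also rests on case report forms, and the protocol mentions eCRF instructions and data entry guidelines. None of these is available here, and they may settle the matter. This reading is reasonable and may be how sites worked. It stands as a limit on the consequence, but no text in the protocol or SAP requires it. Because collection starts after first dose, a worsened condition carried under its old date is a main kind of record that the pre-dose rows would catch.

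A second reply is that Appendix 2 concerns partial dates only. Its title says so, but its first rows classify fully known dates, and a programmer would apply them.

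A third is that the proposed exception may not be programmable, because the documents name one severity and no date of grade change per event. That is fair, and the fix allows for it.

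Some stronger inferences are tempting and fail. A reader might conclude that every event with an early or uncertain start is dropped; missing or ambiguous starts are kept unless the stop date is pre-dose. A reader might conclude that worsening eye toxicity would disappear; it is tabulated in several places without the TEAE filter. A reader might take the planned listing of non-TEAEs as evidence that such records are expected; that label also covers events starting after the window closes.

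**Conclusion.** The contradiction between SAP 19.1 and Appendix 2 is certain from the text. Its effect is conditional: events are lost from the TEAE-only summaries only if a worsened condition was entered with its original, certainly pre-dose onset date. The records remain in the AE listings. The practical exposure is mainly fatigue, hypertension, proteinuria, hypothyroidism and similar conditions without a graded table of their own. The number of events cannot be estimated from the documents, and it is zero if every worsening was a new record dated at the worsening. The documents do not support a claim that safety events were in fact lost, or any specific percentage. This is a minor point, worth correcting because the present rule departs from the SAP's own definition.

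**What to change.** Make Appendix 2 match SAP 19.1. In the three known-start rows that label a pre-dose start as not TEAE, and in the three rows for partial starts that must be pre-dose, add: *unless severity increased on or after first dose and within the TEAE window, then TEAE*. Amending only the known-start rows would leave case 3 unresolved.

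If the eCRF holds only one severity per record, that exception cannot be programmed. In that case, state in the SAP and the eCRF instructions that post-dose worsening is a new AE record whose start date is the date of worsening, and review all AE records with a pre-dose start before database lock.

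The cost is a small amount of programming and data review. The analysis sets, the TEAE window and the efficacy analyses do not change.

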14. PREVIOUS AND CONCOMITANT MEDICATIONS

The protocol indicates that medications including dietary supplements taken from the time of informed consent through the last formal follow-up observational period should be recorded on the Concomitant Medications CRF. All recorded medications will be coded using the WHO drug dictionary version 01 Sep 2015.

Subsequent discussions indicated no interest in medications taken before the first dose of study medication. Therefore, recorded medications that were used on or after C1D1 will be classified as concomitant or post-treatment according to the definitions below; prior medications will be listed but will not be summarized.

Concomitant medications are medications which were used during the period of treatment with study drug, including:

- Medications that started prior to C1D1 and ended (or were ongoing) on or after C1D1
- Medications that started and ended on C1D1
- Medications that started on or after C1D1 and before a decision to discontinue treatment for AGS-16C3F subjects or before the last dose of study medication for axitinib subjects.

Post-treatment (or “post”) medications are medications that began on or after the date of a decision to discontinue study drug for AGS-16C3F subjects or after the last dose of study drug for axitinib subjects.

See Appendix 2 for handling of partial dates for medications. The status of each medication as a concomitant or post-treatment medication will be determined after the imputation of any partial or missing dates.

In cases where it is not possible to determine if a medication was used during or after the treatment period, the medication will be classified as a concomitant medication only.

The number and percent of subjects who used each type of concomitant medication, categorized by ATC Level 1 (Anatomical Main Group), ATC Level 4 (Chemical/therapeutic/pharmacological subgroup), and medicinal product (MP), will be summarized by treatment arm for the FAS, PPS and SAF. Post-treatment (“Post”) medications taken as part of a subsequent cancer treatment regimen for RCC will be summarized similarly and will be presented on a separate table.

All recorded medication data will be listed.

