17.1.2.1. PFS Censoring Rules (Set 1)

The PFS Censoring Rules (Set 1) will be used to manage missing data in the primary analysis of PFS. Under the Set 1 rules, PFS will be right-censored for subjects who meet one or more of the following conditions:

- Subjects with no post-baseline disease assessments (unless death occurred prior to the first scheduled assessment, in which case death will be considered a PFS event)
- Subjects who initiate subsequent anticancer therapy or intervention in the absence of documented progression
- Subjects who die or have disease progression after missing 2 or more consecutively scheduled disease assessment visits
- Subjects who are last known to be alive and progression-free on or before the data cut-off date

For such subjects, PFS will be right-censored according to the conventions described in Table E. These conventions are based on the May 2007 FDA Guidance for Industry “Clinical Trial Endpoints for the Approval of Cancer Drugs and Biologics”.

Table E. PFS Censoring Rules (Set 1): Date of Progression or Censoring

Situation	Date of Progression or Censoring	Outcome
Death before first scheduled disease assessment	Actual date of death	Progressed
Documented disease progression before first scheduled disease assessment	Actual date of disease assessment at which progression was noted	Progressed
Death or documented disease progression between 2 scheduled disease assessments	Actual date of death or actual date of first disease assessment showing documented disease progression, whichever occurs first	Progressed
Missed ≥ 2 consecutive disease assessments immediately prior to death or progression	Actual date of last non-missing disease assessment that is before the missed visits and prior to death and prior to documented disease progression	Censored
No death and no post-baseline disease assessments	Actual date of randomization	Censored
Non-protocol anticancer treatment started prior to death or prior to documentation of disease progression	Actual date of last non-missing disease assessment prior to start of non-protocol anticancer treatment	Censored
Alive and not progressed [1]	Actual date of last non-missing disease assessment	Censored

[1] Without death and without documentation of disease progression; includes subjects who may have discontinued from study prior to death and without documentation of disease progression.

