17.1.2.2. PFS Censoring Rules (Set 2)

PFS Censoring Rules (Set 2) will be used for sensitivity analyses to address potential bias related to the violation of the assumption of non-informative censoring and missing disease assessments. The definition of a PFS event is expanded from the conventional definition of PFS specified in Set 1 rules to include subjects who discontinue protocol treatment, start non-protocol treatment prior to death or progression, or miss ≥ 2 consecutive disease assessments immediately prior to death or progression.

Under the Set 2 rules, the occurrence of a PFS event will be imputed (i.e. not be considered censored) under the following conditions:

- Discontinuation of treatment will be considered a failure of therapy. Therefore, subjects who discontinue therapy without death and without documented disease progression will be counted as an observed PFS event at the time of discontinuation.
- Patients for whom documentation of disease progression or death occurs immediately after ≥ 2 consecutive missed disease assessments will be considered to have had an observed PFS event on the date of the last disease assessment visit without documentation of disease progression prior to the missed visits.
- Patients who use any non-protocol anticancer treatment prior to documented disease progression will be considered to have had an observed PFS event on the start date of the new therapy.

PFS will be right-censored for subjects who meet one or more of the following conditions:

- Subjects with no post-baseline disease assessments unless death occurred prior to the first scheduled assessment (in which case death will be considered a PFS event).
- Subjects who are last known to be alive and progression-free on or before the data cut-off date.

Table F summarizes the handling of missing data and PFS determinations under the Censoring Rules (Set 2).

Table F. PFS Censoring Rules (Set 2): Date of Progression or Censoring

Situation	Date of Progression or Censoring	Outcome
Death before first scheduled disease assessment	Actual date of death	Progressed
Death or documented disease progression between 2 scheduled disease assessments	Actual date of death or actual date of first disease assessment showing documented disease progression, whichever occurs first	Progressed

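### SAP Appendix 2 back-dates incomplete medication start dates with no exception for next-line anticancer therapy, so therapy begun after study treatment can be flagged concomitant and drop out of the subsequent-therapy table

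*SAP*

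**What the plan says.** SAP Appendix 2, in its algorithm for prior, concomitant and post medications, has two general rules for start dates. Rule 5 reads "Impute a partial start date as earliest possible date (i.e. first day of month if day unknown", and uses 1 January when the month is unknown as well. Rule 4 reads "If the start date is missing, assume the medication was ongoing prior to first dose". Rule 1 states what the imputed dates are for: "Use the known actual dates and the imputed dates to derive each medication flag as described in the remaining specifications".

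The flags follow from those dates. POST rule 13 begins "AGS: If (medication start date ≤ date of decision to end treatment) then post='No", with the same comparison against last dose for axitinib. POST rules 15 and 16 cover an absent start: "If the medication start date is missing, assign as post='No". Concomitant rules 10 to 13 give concomitant='Yes' to a drug whose start lies before the decision date or last dose, or whose start is missing and which was not stopped before first dose.

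SAP 14 assigns status after imputation and builds the table of subsequent RCC regimens from post medications. Where timing during or after treatment cannot be determined, "the medication will be classified as a concomitant medication only".

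For PFS, Table E (Set 1) censors for new therapy at "Actual date of last non-missing disease assessment prior to start of non-protocol anticancer treatment". Under Set 2, "Patients who use any non-protocol anticancer treatment prior to documented disease progression will be considered to have had an observed PFS event", dated at the actual start of the new therapy. Section 17 does not say what to do when that start is only partly known.

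**The concern.** Taking the earliest possible start is a reasonable convention for ordinary concomitant drugs. Next-line anticancer therapy normally follows the end of study treatment, so for it the same convention errs in one direction: a start a week or two after stopping is moved to the first of the month, often before stopping.

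Three things depend on this:

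- **Subsequent-therapy table.** It loses exactly the therapies that began soon after treatment ended.
- **Per-protocol set.** Antitumor therapy flagged concomitant resembles PD4, excluded concomitant treatment, which SAP 5.2 lists as a reason for exclusion. The PPS is used for PFS (SAP 17.1.4.1) and for all secondary efficacy endpoints (SAP 17.2).
- **Set 2 dates.** Set 2 needs a start date for the new therapy. With none defined for partial records, a programmer may reach for the only written medication-date rule, which is Appendix 2.

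**Working it through.** The plan states no figure on this point and no rate of incomplete dates, so there is nothing of its own to reproduce. What can be worked out is how often the rules give the wrong flag, given an incomplete date.

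**Inputs.** Rules 4 and 5, concomitant rules 10 to 13 and POST rules 13 to 16 (SAP Appendix 2); the 8-week assessment interval (SAP 3.1); the PFS formula (SAP 17.1.1). Assumption: the reference date (decision to end treatment, or last dose) is equally likely to be any of the 1,461 days of 2017 to 2020, and therapy truly starts L days later.

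**Day missing.** The imputed start is the first of the month in which therapy began. It falls on or before the reference date only if both dates lie in the same month, which has probability of about max(0, 1 − L/30.4). Counting over the 1,461 days, and for the month-missing case below, gives:

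| True lag L (days) | 1 − L/30.4 | Day missing: on or before | Day missing: strictly before | Month also missing: on or before |
|---|---|---|---|---|
| 7 | 0.77 | 77.0% | 73.7% | 98.1% |
| 14 | 0.54 | 54.0% | 50.7% | 96.2% |
| 21 | 0.31 | 31.0% | 27.7% | 94.3% |
| 28 | 0.08 | 8.0% | 4.9% | 92.3% |
| 42 | 0 | 0% | 0% | 88.5% |

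Two dates in one month are at most 31 − 1 = 30 days apart, so a day-only gap cannot cause the error at longer lags.

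The gap between the two day-missing columns is the case where the imputed start equals the reference date. There POST rule 13 gives both post='No' and post='Yes' if the stop date is later, and POST rule 14 gives post='Yes' if the stop is missing. Strictly before, the result is concomitant='Yes', post='No' without ambiguity.

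**Month also missing.** The same argument over a year gives about 1 − L/365.25: 0.98, 0.96, 0.94 and 0.92 for the first four lags, agreeing with the last column.

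**Start missing.** POST rules 15 and 16 give post='No' in 100% of cases.

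**Example.** Randomization 28 February 2017; C1D1 1 March; scans every 56 days on 26 April and 21 June. Progression and the decision to stop fall on 21 June. Next-line therapy starts on 28 June but is recorded as June 2017 only, so the imputed start is 1 June.

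- Flags: 1 June is before 21 June, so concomitant='Yes', post='No', and the therapy is absent from the subsequent-therapy table.
- Set 1: progression on 21 June is day 113 + 1 = 114, and 114/365.25 × 12 = 3.75 months. SAP 17.1.2 ranks a progressed outcome ahead of a censored one when several situations apply, so the event and its date stand.
- Set 2, if the imputed date is borrowed: 1 June is day 93 + 1 = 94, and 94/365.25 × 12 = 3.09 months. Both situations count as events and SAP 17.1.2 takes the shortest time, so the event moves 20 days ahead of the scan that showed progression.
- Sets 3 and 4 censor for new therapy, so the ranking keeps the documented progression there too.

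**The case against.** The strongest reply is that Appendix 2 is not written for PFS. Rule 1 confines the imputed dates to medication flags, SAP Table D sends missing efficacy data to Section 17, and Set 2 refers to an actual start date. That stands. A reader might infer that primary PFS loses events, with the example subject censored at the 26 April scan. The documents do not support it: no section feeds an Appendix 2 date into Table E, and even if one did, the SAP 17.1.2 ranking read literally keeps the progression. The Table E row for new therapy before progression does sit awkwardly with that ranking, and protocol Table 13 has no ranking at all. That is a conflict to reconcile, not evidence that Set 1 events are lost.

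Nor does rule 4 set a missing start to an early calendar date. It assigns no date, so the 100% figure concerns the post flag only.

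It can also be said that SAP 14 openly defaults to concomitant when timing is unclear, that all recorded medications are listed, and that SAP 4.2 expects critical fields to be clean. This makes the error traceable and probably infrequent. It does not make the table right: imputation comes first, so an uncertain date is handled as a determined one. PD4 exclusion is likewise a risk and not automatic, because deviations are recorded in the trial management system (SAP 10) and the sponsor approves set membership (SAP 5).

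**Conclusion.** The point holds for the medication flags. Followed as written, Appendix 2 misclassifies next-line therapy that began after study treatment whenever the imputed start falls before the decision date or last dose, or the start is missing. Given an incomplete date, the share is 77% at a 7-day lag falling to 8% at 28 days if the day alone is missing (74% to 5% excluding exact ties), above 90% at those lags if the month is missing too, and 100% for the post flag if there is no start date. These shares assume reference dates spread evenly over the calendar. The number of subjects affected cannot be given, because the documents state no rate of incomplete dates.

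The consequences are an undercounted descriptive table and a possible wrong PPS exclusion. For PFS the finding is a gap: Section 17 has no rule for a partial therapy start. Set 2 is exposed only if the Appendix 2 date is borrowed to fill it; Set 1 is unchanged under the SAP 17.1.2 ranking.

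**What to change.** Add to SAP Appendix 2:

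> For non-protocol anticancer therapy, a partial start date is imputed as the later of (i) the earliest date compatible with the recorded part and (ii) the day after the decision to end treatment (AGS-16C3F) or the last dose (axitinib), but never later than the last date compatible with the recorded part or the stop date. A fully missing start is queried.

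In the example this gives 22 June: the therapy is flagged post and Set 2 stays at 3.75 months. The cap matters: a start recorded only as March with a decision on 31 March would otherwise be imputed to 1 April, contradicting the record.

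In Section 17, state that this date is used for Sets 1 to 4, and reconcile the SAP 17.1.2 ranking with the Table E new-therapy row. Resolve POST rule 13 when start and reference date coincide. Where an axitinib last dose is itself imputed from the start of a non-study regimen (SAP 15.2.1.1), say which date is derived first, to avoid circularity.

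The cost is a few sentences, one derivation and some queries, with no new data collection. The downside is that a few therapies truly begun just before treatment ended will be dated slightly late, and by more when only the year is known. If treatment stopped before progression was documented, the rule does not settle the order of therapy and progression within the month; such records should be queried.
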